13.5 Description of inclusions and follow-up

Patients pre-included and non-included in the research will be described and compared with included patients. The following will be presented :

- flow chart of the study
- the number of patients included, the inclusions curve (evolution of the number of patients included between the first and last inclusion)

- the theoretical number of visits corresponding to the number of patients included, the real number of visits and the relationship between the two (true number of visits/ theoretical number of visits) are presented for each group.
- the accumulated duration of follow-up is calculated (sum of the time each included patient participates (time between the inclusion date and the date of last news in the research) and the ratio of the accumulated duration of follow-up/expected accumulated duration is presented.

13.6 Characteristics of patients before the start of treatment

Respect of the inclusion criteria and the characteristics of patients pre-included and included in the analysis will be presented:

- respect, non respect, reasons of non-respect of the eligibility criteria (separating minor from major violations / with regard to the inclusion criteria)
- demographic characteristics
- clinical characteristics
- biological/immunological/virological characteristics
- treatment characteristics.

13.7 Study treatments

- number, duration, reasons for stopping treatment/ trial treatment strategy
- duration of follow-up under trial treatment / trial treatment strategy

13.8 Primary endpoint

The main endpoint of the trial is the Sustained Virological Response defined by undetectable plasma HCV RNA (< 12 IU/mL) 12 weeks after cessation of treatment with Grazoprevir / Elbasvir.

- Patients who will be lost to follow-up at PT12 visit and patients who will meet the criteria for interruption of treatment for virological failure will be considered as failures in the analysis of the main endpoint.
- Patients who undergo the treatment up to W8 and with undetectable HCV-RNA at PT12 will be considered as successful
- Patients who stop treatment prematurely for intolerance and with undetectable HCV-RNA at PT12 will be considered as successful.
- Patients who cannot undergo the PT12 visit and with undetectable HCV-RNA at W48 will be considered as successful.

13.9 Secondary endpoints

HCV virological assessment

- Median (+IQR) of log HCV RNA at W4, W8, PT4 and PT12, globally and according to genotypes.
- Rate of HCV RNA (<12 IU/mL) at W4, W8, PT4 and PT12, globally and according to genotypes.
- Odds ratio of factors associated with SVR12.
- Number of HCV (NS5A and NS3/4) resistance mutations in patients with virological failure.
- Rate of adherence and quality of life measured by specific scales using self questionnaires.
- Number of patients with positive HCV RNA per hundred months follow-up.

HIV virological assessment

- Median (+IQR) of log HIV RNA at D0 and PT12
- Median (+IQR) of CD4 and CD8 cell counts (absolute count, percentage and CD4/CD8 ratio) at D0 and PT12.
- Number of AIDS-defining clinical or biological events using CDC classification (95% CI).

Safety assessment

- Number of adverse clinical and biological events that occur during the treatment and up to 48 weeks after the end of the treatment (95% CI).

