1 SYNOPSIS

N°EudraCT / ClinicalTrials ID : 2016-001125-13

Title of the study

Pilot study - Short duration therapy of acute hepatitis C genotypes 1 or 4: efficacy and tolerability of grazoprevir 100mg/elbasvir 50mg during 8 weeks

Short title SAHIV

Sponsor

IMEA (Institut de Médecine et d'Epidémiologie Appliquée – Fondation Léon M'Ba)

CHU Bichat-Claude Bernard

[name], France

[contact] - Fax: [name]

Coordinating investigator **Pr [name]**
Sorbonne-Universités, INSERM UMR-S1136 – IPLESP
Hôpital St Antoine, [name] - France

Participating country **France (See list of investigator sites in Appendix B3)**

Objectives/ Endpoints

Objectives	Endpoints
Primary	
To assess the rate of sustained virological response (SVR) 12 weeks after 8 weeks of oral treatment with grazoprevir 100mg/elbasvir 50mg (MRK-combo) in patients with acute hepatitis C genotype 1 or 4.	SVR rate defined by an undetectable plasma HCV RNA (<12 IU/mL) 12 weeks post-treatment (SVR12).
Secondary	
HCV virological assessment	
To describe the HCV virological response (W4, W8, PT4 and PT12) as a whole and according to genotypes.	- Median (+IQR) of log HCV RNA at W4, W8, PT4 and PT12, globally and according to genotypes. - Rate of HCV RNA (<12 IU/mL) at W4, W8, PT4 and PT12, globally and according to genotypes.
To study the prognostic factors associated with SVR12 (PT12).	Odds ratio of risk factors associated with SVR12 (PT12).
To assess the emergence of resistance in case of virological failure (HCV RNA ≥12 IU/mL).	Number and description of HCV (NS5A and NS3/4) resistance mutations in patients with virological failure.
To describe treatment adherence and quality of life during the course of the study	Rate of adherence and quality of life measured by specific scales using self questionnaires.
To evaluate the incidence of HCV reinfection at 1 year (PT48).	Number of patients with positive HCV RNA per hundred months follow-up.
To evaluate the sensitivity of HCV rapid testing (using the Oraquick HCV rapid antibody test) in patients with first acute Hepatitis C.	To evaluate the proportion of positive rapid tests

HIV virological assessment (only for HIV co-infected patients)	

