2 FOLLOW-UP TIMETABLE

	Screening ^a D-14	D0	W4	W8	PT4 SVR4	PT12 SVR12	PT48 SVR48
Time windows (days)	+7 or -14 (from D-28 to D-7 before D0)	/	+/-7	+/-7	+/-7	+/-7	+/-7
Patient instructions	/	No medication intake before coming		/	/	/	/
Eligibility criteria / Informed Consent	X						
Clinical examination (including sitting blood pressure, weight, drugs*, tobacco* and alcohol consumption*) *Only at screening	X	X	X	X	X	X	X
Concomitant treatments (After 30 days post-study treatment, only medications associate with HCV and HIV treatment)	X	X	X	X	X		
Serious or not serious adverse events (until 30 days after the end of study treatment)	X	X	X	X	X		
HCV Genotype	X						
HCV RNA	X	X	X	X	X	X	X ^b
HCV antibodies (ELISA and Rapid test) ^d		X ^d	X ^{d,e}				
HIV antibodies (only for HCV mono-infected patients)	X						
HBs Ag ^c	X						
AST, ALT, total and conjugated bilirubin, GGT, ALP	X	X	X	X	X	X	X
CD4, CD8 (only for HIV co-infected patients)		X				X	
HIV RNA (only for HIV co-infected patients)		X				X	
FBC, platelets	X	X	X	X	X	X	
Blood creatinine and creatine clearance (CKD-EPI)		X	X	X	X	X	
Beta-HCG (Screen) or urinary pregnancy test (if applicable)	X	X	X	X	X	X	
QUESTIONNAIRES							
Adherence self-questionnaire			X	X			
“Quality of life” Questionnaire		X				X	
SAMPLES FOR BIOBANK							
Blood for serum collection (7/8 mL in dry tubes)		X	X	X	X	X	X
Blood for plasma collection (7/8 mL in EDTA tubes)		X	X	X	X	X	X
PHARMACY							
Treatment Dispensation/Return (Grazoprevir / Elbasvir)		X		X			

^a Screening visit will be only performed if the biological results needed to check the eligibility criteria are not available in the patient medical file and dated between 1 to 4 weeks before D0 (≤ 3 months for Ag HBs). In this case, the clinical examination and the signature of informed consent could be done at D0.

^b In case of positivity, a phylogenetic analysis will be performed in order to differentiate a late relapse from reinfection.

^c Only done, if there is no result ≤ 3 months before D0 in the medical file.

^d Only for patients with first acute infection

^e Only done if HCV antibodies results are negative at Day 0.

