7.1 Inclusion criteria

1. Adult ≥ 18 years
2. A recent acute HCV infection or reinfection (see definition below) occurred within 6 months prior screening:

An acute HCV infection is defined by:

- a. HCV RNA was detectable within 6 months after a negative HCV RNA or HCV serology test.

OR

- b. Detectable HCV RNA and an acute clinical hepatitis occurred within 5 months prior to the screening visit.

Clinical Hepatitis is defined by:

- ALT ≥ 250 IU/L with normal ALT within the preceding 8 months,

or

- ALT ≥ 500 IU/L with either no measured ALT or with abnormal ALT within the preceding 8 months.

OR

Patients having reported a risk factor for HCV contamination (traumatic sexual intercourse, intranasal, rectal or intravenous drug use) inferior or equal to 6 months. HCV reinfection is defined by:

- a. Documented *de novo* infection after prior clearance after treatment or spontaneously,
 - After-treatment clearance is defined by one negative HCV RNA ≥ 6 months after end of treatment.
 - Spontaneous clearance is defined by two negative HCV RNA a minimum of 6 months apart.

OR

- b. Documented infection with a new viral strain, confirmed by phylogenetic or genotypic analysis.
3. Infection with HCV genotype 1 or 4 (confirmed at screening visit or by using a previous biological test performed 1 to 4 weeks before D0)
4. Plasma HCV-RNA ≥ 1000 UI/mL (confirmed at screening visit or by using a previous biological test performed 1 to 4 weeks before D0)
5. Confirmed HIV infection (only for HIV co-infected patients)
6. Without HIV treatment or with an acceptable stable HIV treatment for at least two weeks (See section 8.3 of the protocol, only for HIV co-infected patients)
7. Body weight ≥ 40 kg and ≤ 125 kg
8. Female patients with child-bearing potential and their heterosexual partners must use adequate contraception from the date of screening until 30 days after administration of the last dose of study drug. Male participants must agree to consistently and correctly use a condom, while their female partner must use adequate contraception from the date of screening until 30 days after administration of the last dose of study drug
9. Informed and signed consent
10. Patients with Health insurance (Sécurité Sociale or Couverture Médicale Universelle)

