9.9 HCV virologic failure criteria

The following criteria will be considered evidence of HCV virologic failure for the purposes of patient management:

- Confirmed increase from nadir in HCV RNA (defined as 2 consecutive HCV RNA measurement of > 1 log₁₀ IU/mL above nadir) at any time point during study drug treatment.
- Confirmed HCV RNA ≥ 100 IU/mL (defined as 2 consecutive HCV RNA measurements ≥ 100 IU/mL) after HCV RNA < LLOQ during study drug treatment.

When confirmatory testing is required, it should be completed as soon as possible and the subject should remain on study drug treatment until the virologic failure criteria has been confirmed. Subjects meeting the virologic failure criteria will be discontinued from study drug and will continue to be followed in the Post-Treatment Period for the emergence and persistence of resistant viral variants until 48 weeks post-treatment (PT48).

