13.2 Sample size determination

Since the study is single-arm, non-comparative in design, the sample size will be based on statistical precision and not a comparative statistical test. The sample size should allow a precision of <30% absolute difference between lower and upper bounds of the Clopper-Pearson 95%CI. The expected SVR12 rate is 80% from previous studies, hence bounds are calculated from point estimates of SVR12 $\geq 80\%$. A total 30 patients are necessary to fulfill the statistical criteria above.

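### The reinfection endpoint counts every patient with positive HCV RNA, so viremic treatment failures are reported as reinfections

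*Combined protocol and SAP*

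**What the plan says.** The synopsis and Section 4.2 set a secondary objective on how often patients are reinfected with HCV in the year after treatment, assessed at PT48. The synopsis table pairs it with the endpoint "Number of patients with positive HCV RNA per hundred months follow-up". Sections 6.2 and 13.9 use the same words. Section 13 does not define the event further.

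Four other places bear on it:

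- **Section 9.9:** patients who meet the virologic failure criteria stop study drug but "will continue to be followed in the Post-Treatment Period for the emergence and persistence of resistant viral variants", up to PT48.
- **Footnote b of the timetables (Sections 2 and 9.1) and Section 9.7:** "In case of positivity, a phylogenetic analysis will be performed in order to differentiate a late relapse from reinfection". Footnote b is attached to PT48 only; Section 9.7 covers PT4, PT12 and PT48.
- **Section 7.1:** reinfection is defined for eligibility only, by new infection after clearance or, alternatively, by "Documented infection with a new viral strain, confirmed by phylogenetic or genotypic analysis". For the first route, "After-treatment clearance is defined by one negative HCV RNA ≥ 6 months after end of treatment".
- **Section 13.5:** accumulated follow-up is the "time between the inclusion date and the date of last news in the research", summed over included patients. No denominator is given for the reinfection endpoint itself.

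**The concern.** The objective asks about new infections, but the endpoint counts viremia. A patient who never cleared the virus, or who relapsed with the original strain, has positive HCV RNA after treatment and meets the endpoint as stated. The figure offered as a reinfection rate would therefore rise and fall with treatment failure as well as with reinfection, and would be above zero whenever a viremic failure is followed up, even if nobody is reinfected.

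The protocol's background stresses high reinfection in this population, so the figure will be read as a reinfection rate. The primary endpoint is not touched.

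**Working it through.** The plan gives no expected reinfection rate, event count or precision for this endpoint, so there is no figure of its own to reproduce. What follows illustrates the size of the problem.

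**Inputs from the documents.** 30 patients and an expected SVR12 of 80% (Section 13.2: "The expected SVR12 rate is 80% from previous studies"); 56 weeks of follow-up from D0, 48 of them after treatment (Section 5.2 and synopsis); up to 21% reinfected within 3 years (Section 3.2.1, for HIV-infected men who have sex with men; the trial also enrols mono-infected patients).

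**Assumptions.** Full follow-up; all failures viremic after treatment; positive means positive after treatment; constant reinfection hazard; reinfection before PT12 not counted as a treatment failure; 1 month = 30.44 days.

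**Denominators.** With none stated, two are used:

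- from inclusion, as in Section 13.5: 56 × 7 / 30.44 = 12.88 months; × 30 = 386.3 months
- post-treatment only: 48 × 7 / 30.44 = 11.04 months; × 30 = 331.1 months

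**Step 1: no reinfection at all (true rate 0).** Rate = 100 × failures / months.

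| Viremic failures | 386.3 months | 331.1 months |
|---|---|---|
| 6 (80% SVR12) | 1.55 | 1.81 |
| 3 (90%) | 0.78 | 0.91 |
| 1 | 0.26 | 0.30 |

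**Step 2: reinfection at the cited figure.** Hazard = −ln(1 − 0.21) / 36 = 0.006548 per month, or 0.655 per 100 months. Risk over 48 weeks = 1 − exp(−0.006548 × 11.04) = 6.97%. Expected patients counted = 30 × SVR12 × 0.0697 + 30 × (1 − SVR12). At 80%: 24 × 0.0697 + 6 = 7.67.

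| SVR12 | Patients counted | Rate, 386.3 months | Ratio to 0.655 | Rate, 331.1 months | Ratio to 0.655 |
|---|---|---|---|---|---|
| 80% | 7.67 | 1.99 | 3.03 | 2.32 | 3.54 |
| 90% | 4.88 | 1.26 | 1.93 | 1.47 | 2.25 |
| 95% | 3.49 | 0.90 | 1.38 | 1.05 | 1.61 |

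Counting reinfections only from PT12 (8.28 months at risk) leads to the same conclusion: 1.27 expected reinfections, (1.27 + 6) / 386.3 = 1.88 per 100 months, against 1.27 / (24 × 8.28) = 0.64.

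**Step 3: sensitivity.**

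- Half the reinfection figure (10.5% in 3 years, hazard 0.003081, 48-week risk 3.34%), 386.3 months: 5.7-, 3.3- and 2.1-fold at 80%, 90% and 95% SVR12.
- Failures lost at end of treatment, 80% SVR12, 21% figure: 2 of 6 lost, 5.67 / 364.3 = 1.56 (2.4-fold); 4 lost, 3.67 / 342.2 = 1.07 (1.6-fold); all 6 lost, 1.67 / 320.1 = 0.52 (0.8-fold, no inflation).

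**Step 4: does a corrected definition recover the true rate?** At 80% SVR12 and a true rate of 0.655, the 24 at-risk patients with events dated at the midpoint between tests give 1.673 / 255.6 = 0.655. Dating at the first positive test gives 1.673 / 261.1 = 0.641. If the six failures are relapsers censored at the midpoint before PT4, they add 2.8 months and the rate is 0.648. Leaving six never-cleared patients in the denominator would give 0.52.

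**The case against.** The best reply is that context supplies the missing definition. The synopsis sets the endpoint beside the reinfection objective, and the protocol orders phylogeny to tell late relapse from reinfection. Moreover, a fully literal reading would count all 30 patients, since entry requires HCV RNA of at least 1000 IU/mL (30 / 386.3 = 7.8 per 100 months). If context removes baseline positives, why not known failures?

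Reading positive as positive after treatment is a concession to the plan. Removing failures as well needs a classification rule, and Section 13 has none: it does not make the phylogenetic result decide who is counted, place recurrences that cannot be sequenced, or say who contributes time. The planned test shows that the data will exist, not that the endpoint uses them.

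The eligibility definition cannot simply be carried over. Its after-treatment route needs a negative RNA at least 6 months after treatment, and no RNA test is scheduled between PT12 and PT48. The new-strain route is the usable one.

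Three points on the other side stand. The threefold figure depends on 80% SVR12 and on failures being followed; Section 3.3 hypothesises at least 80%, and Section 13.8 counts losses at PT12 as failures. The endpoint is descriptive in a 30-patient pilot, and an interval around the corrected rate could well include the inflated value. Start of time at risk and event dating are also partly matters of choice. None of this removes the bias; it limits its practical weight and argues for fixing the choices before analysis.

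**Conclusion.** The concern holds. The endpoint as defined does not measure reinfection, and every viremic failure with a post-treatment result raises it. That needs no outside rate: six such failures and no reinfection give 1.55 per 100 months on time from inclusion, or 1.81 on post-treatment time.

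On the cited 21% in three years, the overstatement on time from inclusion runs from about 1.4-fold at 95% SVR12 to 3.0-fold at 80%. It grows if reinfection is rarer, and shrinks or vanishes if failures are lost before a post-treatment RNA test. These sizes rest on the assumptions listed above. The point is secondary but should be corrected before analysis.

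**What to change.** Rewrite the endpoint in the synopsis, Section 6.2 and Section 13.9:

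- **At-risk set:** patients with undetectable HCV RNA (<12 IU/mL) at end of treatment or a later post-treatment visit. Never-cleared patients contribute neither events nor time.
- **Event:** later HCV RNA ≥12 IU/mL with a strain shown by phylogenetic or genotypic analysis to differ from D0.
- **Person-months:** from end of treatment (or first post-treatment undetectable RNA, if later) to reinfection, relapse or last HCV RNA test.
- **Event date:** a fixed rule for the PT12 to PT48 gap, for example the midpoint between last negative and first positive test.
- **Other recurrences:** same strain is relapse; no usable sequence is undetermined. Report both separately, with a sensitivity analysis counting undetermined cases as reinfections.
- **Precision:** an exact 95% CI.

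Reconcile footnote b with Section 9.7 on which visits trigger phylogeny. State how the endpoint relates to Section 9.10, which labels any detectable RNA at PT12 or PT48 as virological failure. Acknowledge that requiring prior undetectable RNA is narrower than the either/or definition in Section 7.1: a new strain in a never-cleared patient falls outside the event.

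The cost is protocol and SAP wording. The RNA tests, phylogeny and banked D0 samples are already planned. Two drawbacks remain. Events will be few and the interval wide: 2 events in 256 months give 0.78 per 100 months, exact Poisson 95% CI 0.09 to 2.82. And reinfection with a strain indistinguishable from D0 would be classed as relapse.

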5.0	19/01/2018	2	
1- In order to accelerate patient recruitment, it was decided to modify the protocol as follows:
 
 - Including mono-infected patients with acute HCV infection (genotypes 1 or 4), - Allowing to include patients having reported a risk factor for HCV contamination (traumatic sexual intercourse, intranasal, rectal or intravenous drug use) inferior or equal to 6 months, - Reducing the sample size to 30 patients, - Extending inclusion period by three months, 
2- [name], infectious disease physician at Saint-Antoine hospital will replace [name] and will perform the following tasks:
 
 - Principal investigator of Saint Antoine hospital study center - Scientific committee member - Study pharmacovigilance management 
3- [name], the study coordinating investigator, has been named as Professor.
 
4- These modifications resulted in a revised study title, informed consent form and study timetable.

LIST OF ABBREVIATIONS AND DEFINITION TERMS

AE	Adverse Event
AIDS	Acquired Immune Deficiency Syndrom
ALP	Alkaline Phosphatase
ANSM	Agence Nationale de Sécurité du Médicament et des produits de santé
ALT	Alanine aminotransferase (SGPT)
ART	Anti Retroviral Treatment
AST	Aspartate aminotransferase (SGOT)
CI	Confidence Interval
CPP	Comité de Protection des Personnes
CRA	Clinical Research Associate
DSMB	Data and Safety Monitoring Board
EC	Ethic Committee
eCRF	Electronic Case Report Form
FBC	Full blood count
GCP	Good Clinical Practice
GGT	Gammaglutamyl-transpeptidases
HCV	Hepatitis C Virus
HIV	Human Deficiency Virus
ITT	Intent-to-treat
IU	International Unit
LLOQ	Lower limit of quantification
PP	Per Protocole
RNA	RiboNucleic Acid
SAB	Scientific Advisory Board
SAE	Serious Adverse Event
SmPC	Summary of the Product Characteristics
SUSAR	Suspected Unexpected Serious Adverse Event
SVR	Sustained Virologic Response
TSH	ThyreoStimuline Hormon

MAIN CONTACTS

Sponsor

IMEA (Institut de Médecine et d'Epidémiologie Appliquée – Fondation Léon M'Ba)
 CHU Bichat-Claude Bernard
 [name], France
 [contact] - Fax: [name]

Methodology and Management Centre

Pr [name], coordinating investigator

Sorbonne-Universités, INSERM UMR-S1136 – IPLESP
 Hôpital St Antoine
 [name] - France
 [contact] - Fax: [name]
 Email: [contact]

[name], methodologist and biostatistician

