- To assess the emergence of resistance in case of virological failure (HCV RNA \geq 12 IU/mL).
- To describe treatment adherence and quality of life during the course of the study.
- To evaluate the incidence of HCV reinfection at 1 year (PT48).
- To evaluate the sensitivity of HCV rapid testing (using the Oraquick HCV rapid antibody test) in patients with first acute Hepatitis C.

HIV virological assessment (only for HIV co-infected patients)

- To describe the evolution of HIV parameter during treatment (CD4 count and HIV-RNA).

Safety assessment

- To describe all the clinical events occurred during the study course

5 **METHODOLOGY**

5.1 **General design of the research**

Non-randomized, single arm, multicenter, open-label, Phase IIb pilot study conducted in France.

5.2 **Research milestones**

- Trial start date: Beginning 2017
- Enrolment period: 9 months
- Subject participation duration: screening (1 to 3 weeks before D0), then 56 weeks of follow-up → approximately 60 weeks maximum
- Total trial duration: 24 months
- Estimated study completion date: Beginning 2019

The end of the trial corresponds to the date of the last visit of the last patient.

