13.3 Statistical methods

- **Qualitative variables**

Qualitative variables will be described in terms of numbers of patients, percentages and confidence intervals.

- **Quantitative variables**

Quantitative variables will be described in terms of populations, medians, range and interquartile range or means, standard deviations and confidence intervals of the mean.

- **Variables of the type 'Time to onset of an event'**

The risk of the first onset of events of interest will be described in terms of probability of onset and confidence intervals with the Kaplan-Meier method. The date of origin is the date of inclusion in the research and the time to onset is the difference between the date of diagnosis of the event and the date of inclusion.

A graphic representation will be associated with the results of the analyses whenever possible.

- **Software used for the statistical analysis**

The analyses will be done using STATA® software for usual statistical analyses.

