13.4 Population analysed

All patients included in the study, apart from patients who present at least one of the following conditions:

- patients who have never taken treatment,
- patients who have withdrawn their consent,
- patients included erroneously with contra-indications to the treatment of the study or without indication to be treated,

constitute the modified intent-to-treat (ITT) population and will be analysed.

Deceased patients and patients lost to follow-up will be included in the analysis until the time of their death/last news.

The decision to exclude a patient from the analysis is made jointly with the Scientific Advisory Board following the recommendations of the independent committee after the collection of the data by the Methodology and Management Centre, without knowing the evolution of the patient after inclusion.

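### CD4, CD8 and their ratio are summarised as separate medians at D0 and PT12; adding the within-patient change would describe their evolution more precisely at almost no cost (minor)

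*Combined protocol and SAP*

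**What the plan says.** The HIV objective in section 4.2 and the synopsis is "To describe the evolution of HIV parameter during treatment (CD4 count and HIV-RNA"). The measure attached to it, repeated in the synopsis, section 6.2 and section 13.9, is "Median (+IQR) of CD4 and CD8 cell counts (absolute count, percentage and CD4/CD8 ratio) at D0 and PT12".

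Section 13.3 sets the general method: "Quantitative variables will be described in terms of populations, medians, range and interquartile range or means, standard deviations and confidence intervals of the mean". On the analysis set, section 13.4 adds: "Deceased patients and patients lost to follow-up will be included in the analysis until the time of their death/last news".

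The timetable in section 2 schedules CD4 and CD8 at D0 and PT12, in co-infected patients only, so each patient who attends both visits supplies a pair. Nowhere do the documents mention a change from baseline, an interval for a change, or a summary restricted to patients with both values. Section 13.8 has a rule for a missing PT12 visit, but it applies to SVR12 only.

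**The concern.** Evolution is a change over time, and the planned output is two cross-sectional pictures. Three things follow.

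- The IQR at each visit shows how much patients differ from one another. It says little about how far they moved, and no figure conveys the uncertainty of the movement.
- Each patient's two values are positively related. Separate medians use that relation less well than the paired differences do.
- Patients lost before PT12 can be in the D0 median and not in the PT12 median. If they differed in CD4 at D0, part of the gap between the medians reflects who remained.

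At stake is how well the report can say whether CD4 moved in a small subgroup. Its size is not stated. It cannot exceed the total of 30 patients and may be smaller, since amendment 2 admitted mono-infected patients.

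**Working it through.** **Plan's own figure.** None exists for CD4 or CD8. The total of 30 was set on the precision of SVR12 and serves here only as a ceiling on the co-infected subgroup.

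**Assumed inputs** (the documents give none): CD4 SD σ = 250 cells/mm3 at each visit, normal values, D0–PT12 correlation r = 0.8 (range 0.7 to 0.9), n = 25 co-infected patients with complete data.

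**Step 1: standard error of the change, three ways.**

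- Mean paired change: σ√(2(1−r)/n) = 250 × √(0.4/25) = 31.6 cells.
- Median paired change: about √(π/2) times that for normal data, 1.253 × 31.6 = 39.6. Simulation gives 39.3.
- Difference of the two visit medians: √[2 × (π/2) × (σ²/n) × (1 − (2/π)·arcsin r)]. With σ²/n = 2,500 and arcsin 0.8 = 0.927, this is √(3.1416 × 2,500 × 0.410) = 56.7. Simulation gives 55.5.

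The like-for-like comparison is median against median: 55.5/39.3 = 1.4. At n = 25 the simulated ratio is 1.28 (61.9 against 48.2) for r = 0.7 and 1.67 (46.2 against 27.7) for r = 0.9. A separate simulation with SD 200 and n = 20 gave 57 against 48 at r = 0.6 (ratio 1.2) and 47 against 34 at r = 0.8 (ratio 1.4).

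**Step 2: a constructed case of a hidden change.** Seven patients have D0 values 300, 400, 500, 600, 700, 800, 900 and PT12 values 350, 450, 550, 600, 750, 850, 950. Six of the seven gain 50 cells. Both visit medians are 600; the median paired change is +50.

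**Step 3: a constructed case of a false change.** Six patients have D0 values 300 to 800 in steps of 100. Nobody changes, and the two lowest are lost. The D0 median is (500 + 600)/2 = 550. The PT12 median of 500, 600, 700, 800 is 650. The apparent rise is 100; the paired change is 0.

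**Step 4: false rise with realistic spread.** Simulation with n = 25, SD 250 and no within-patient change gives this mean apparent rise in the median:

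| Lost of 25 | Loss unrelated to CD4 | D0 CD4 lower by 150 | D0 CD4 lower by 250 |
|---|---|---|---|
| 1 | 0 | 6 | 9 |
| 2 | 0 | 11 | 18 |
| 4 | 0 | 23 | 36 |

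**Step 5: does pairing remove the bias?** Not fully. In the simulation with SD 200, n = 20, no true change and 20% loss concentrated in low CD4, separate medians showed about +21 to +31 cells. The paired change in completers showed about −15 to −4. At r = 0.6 the two biases are of similar order (+21 and −15); at r = 0.9 the paired bias is much smaller (+31 and −4).

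**The case against.** The objective asks for a description, and it does not say that evolution is meant patient by patient. Medians at two visits are a coarse but recognisable description. With complete data and a common shift they are unbiased for the change and only less precise. Section 13.3 also allows means, and with complete data the difference of visit means equals the mean paired change. That stands, but the CI of each visit mean is still not a CI for the change, and sections 6.2 and 13.9 commit to medians.

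Loss may be small. Section 9.11 keeps patients who stop treatment in follow-up, section 7.2 excludes those judged unlikely to keep to the timetable, and section 13.5 reports a flow chart and the ratio of actual to theoretical visits, so attrition will be visible. That different patient sets will be compared is inferred from the general rule in 13.4; the plan does not state it for CD4. Both values are collected, so the paired summary could be produced at reporting even if the protocol says nothing. All of this stands and keeps the point small.

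A reader might infer that the plan forfeits power to detect a CD4 fall. The documents do not support that: they plan no CD4 test, and section 13.2 bases the sample size on precision and not on a comparative test.

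**Conclusion.** The point holds as a minor improvement. For an objective about evolution, the plan commits only to two separate medians, without a change score, an interval for the change or a both-visits set. Under the assumed SD of 250, n = 25 and r = 0.8, the difference of medians has a standard error about 1.4 times that of the median paired change (about 55 against 40 cells). Selective loss of 1 to 4 of 25 patients would add a false rise of about 6 to 36 cells.

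Two stronger readings should be resisted. Setting 55 against the 32 cells of the mean paired change overstates what pairing alone gains, because it also switches from median to mean. And the documents do not show that the visit medians will be biased: that needs losses related to CD4, for which they give no figure, and the bias is nil otherwise.

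The SD, correlation, subgroup size and loss pattern are all assumptions. The primary endpoint is not affected.

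**What to change.** In section 13.9, section 6.2 and the synopsis, keep the visit medians and add the within-patient change from D0 to PT12 for CD4 and CD8 (absolute count and percentage) and the CD4/CD8 ratio, in co-infected patients with both values. Report:

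- the median and IQR of the change, and its mean or Hodges-Lehmann estimate with a 95% CI;
- the number of pairs, and the D0 and PT12 medians for that same set;
- the D0 median of patients without a PT12 value.

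The cost is a sentence in each of the three places and a few table lines, with no new samples, visits or patients. The paired summary leaves out patients without PT12 and can still be biased if loss depends on CD4; the last item lets the reader judge that. It is best added before the data are examined.
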